In our preliminary proof of principle study, we developed and tested a passive robotic system in 21 healthy subjects (aged 26.2, SD 1.2 yrs). A passive robotic arm was developed for supporting and monitoring arm motion and combined with a simple virtual reality pick-and-place game (Srör et al. 2018). Software was developed for integrating input from the robotic arm and a Kinect camera. The software includes a pick-and-place VR game, game success feedback, and motion feedback with and without JEA. Individuals were assigned to a training group with or without EA and performed one 30 min training period. There was no difference between groups in terms of the success rate of hitting the targets. The group training with EA tended to work longer and be more motivated. The application was found to be acceptable to healthy individuals, to enhance motivation to exercise and not to cause fatigue or any adverse effects (Srör et al., 2018; 2019a; 2019b).

The next phases of the study are to investigate the effects on learning with JEA feedback in healthy subjects, and then to test the JEA feedback effect in patients with stroke.

In two separate studies, we will test 24 healthy subjects and 24 patients who have moderate-to-severe stroke (spasticity + some arm movement). Testing of the healthy subjects will be done in Canada and testing of patients will be done in two countries (Israel-Soroker Hospital, Beer-Sheva; Canada-Jewish Rehabilitation Hospital, Laval/Montreal). The motivation for testing the application in patients at two sites is to assess the feasibility of conducting a multi-site study using this technology.

In both studies: Subjects will be randomly allocated to two equal groups. One group (control) will receive regular feedback and the other group will receive JEA feedback (randomized with catch trials).

Subjects will perform ~30 min of target reaching with their non-dominant/affected arm, 3 times in one week, with a minimum of 1 day between sessions. Rest periods will be provided when needed to avoid subject fatigue. In the experimental group, target locations will be tailored to coincide with active control range limits determined at the beginning of each session. In the stroke group, workspace extensions will be added as active range increases (i.e., exercise progression) for patients receiving JEA feedback.

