Session 1 (1 hour and 15 min) will include a Reaching Pre-Test of 10 trials to a fixed target (see below), reaching training and evaluation of perceived exertion. Session 2 (1 hour) will include the evaluation of the TSRT in the stroke group, reaching training and perceived exertion rating. Session 3 (2 hours) will be the same as Session 2 but the last 10 trials of Session 3 will be done to a fixed target (Post-Test). Following Session 3, there will be a pause of 1 hour after the training and then a Reaching Follow-up Test of 10 trials to a fixed target will be done. In addition, the stroke group will undergo a clinical evaluation including determination of the elbow flexor TSRT angle prior to Session 1 and another clinical evaluation following Session 3.

For Study 1, the primary outcome measures are change in the index of performance (IP), which is a measure of reaching efficiency (Takeda et al., 2019).

For Study 2, the primary outcome measures are the same as those for the healthy group as well as the area of the active control workspace based on the TSRT and spasticity. The **secondary outcome measures** are the change in the FMA-UL and patient effort according to the Borg scale.

Evaluations for Study 2:

Clinical evaluation sessions: Clinical assessments will be conducted by a blinded assessor before (Pre-test) and after (Post-test) the last training session. In the Pre and Post-test sessions, all of the following assessments will be done.

Arm motor impairment: **i) Voluntary arm motor ability and coordination** will be evaluated using the valid (Berglund and Fugl-Meyer 1986) and reliable Fugl-Meyer Arm Assessment (FMA; Fugl-Meyer et al. 1975) that measures reflexes, volitional movements and UL

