calculations of Kalman gains for elbow and wrist also account for shoulder and elbow error covariance respectively. Segment lengths are updated after each measurement step. Objects to be reached in VR are determined before training based on the subject's arm range of motion. The RANSAC algorithm (Fischler and Bolles 1981) is used to fit the recorded arm positions into the plane to reduce measurement errors.

Subjects and subject recruitment. Participants will be allocated by random numbers to either an *experimental group* that will receive JEA feedback (randomized with catch trials) or a *control group* that will receive no JEA feedback. **Blinding:** The sequence of allocation will be concealed from those assigning participants to groups until the moment of assignment, to prevent them from consciously or unconsciously influencing which participants are assigned to which groups. Participants will also be blinded to group allocation. Finally, evaluators will be blinded by concealing participant group allocation.

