Patients will be recruited through well-established procedures at the JRH. Potential participants will be identified from chart or database review and sent a letter of information describing the study. If they are interested, they will be directed to contact the research assistant by phone or email who will schedule them for a screening interview. Healthy subjects will be recruited from the community with the help of information flyers posted on bulletin boards. Subjects will participate after signing informed consent forms approved by the Center for Interdisciplinary Research in Rehabilitation (CRIR) Ethics Committee. Handedness will be measured for both studies with the Edinburgh Handedness Inventory (Oldfield 1971) but for Study 2, both right- and left-handed subjects will be included since hemispheric dominance is not expected to influence results. For Study 1, healthy women and men will be included who 1) are between the ages of 18-75 yrs; 2) have normal or corrected-to-normal vision; and 3) are able to provide informed consent. For Study 2, women and men will be included who 1) sustained a first cortical/sub-cortical ischemic/hemorrhagic stroke <1 yr previously and are medically stable; 2) are aged 18-75 yrs to minimize confounding effects of age-related changes in muscular responses; 3) are no longer receiving treatment; 4) have arm paresis (Chedoke-McMaster Arm Scale of 2-6 /7; Gowland et al. 1993) but are able to perform voluntary elbow movement of at least 30° per direction; 5) have mild-moderate elbow flexor spasticity; and 6) are able to provide informed consent. Subjects will be excluded if they have/are: 1) other major neurological neuromuscular/orthopaedic/pain problems that may interfere with task performance; 2) major cognitive deficits (<26 on Montreal Cognitive Assessment; Nasreddine et al. 2005) or 3) depression (> 14 on Beck Depression Inventory II; Beck et al. 1988; 1996).

[figure not shown]

Fig. 3. UL model based on the Kinect II skeleton (left) and explanation of the extended Kalman filter (right) to improve motion tracking accuracy.

Data analysis

For Study 2, data from Canada will be combined with those from Israel for a total of 12 subjects per group.

To address Hypothesis 1, we will compare the change in the IP between the Pre-Test and the Post-Test as an indicator of motor improvement and the change from Post-Test to Follow-Up as an indicator of motor learning using paired t-tests after verifying for data normality.

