To address Hypothesis 2, changes in the area of the active control workspace and clinical scores will be compared between groups using paired t-tests after verifying for data normality.

Knowledge translation

The preliminary results will primarily be used to inform the design of a full randomized controlled trial. However, preliminary results will be shared with clinicians at both sites and by oral or poster presentations at local, national or international meetings.

Participating researchers

[name] is a 1st year Master's student in the Integrated Program of Neuroscience at McGill University. **[name]** is Professor in the School of Physical and Occupational Therapy in the Faculty of Medicine at McGill University. She has pioneered many innovations in the area of upper limb rehabilitation, including identification of underlying motor control deficits at the joint and interjoint level, measurement of spasticity, incorporation of VR training interventions and the distinction between compensation and recovery. **[name]** is an Associate Professor in the Department of Industrial Engineering and Management at Ben-Gurion University of the Negev. She leads the Telerobotics laboratory where robotic motion control, learning, and interaction methodologies are developed and assessed. [name] has applied advanced mathematical methods for modeling and analysis of arm motion in healthy subjects and in patients with stroke. **[name]** is a Senior Lecturer in the Department of Physiotherapy who has been studying human movement in health and in disease for over a decade, publishing in journals that are either specific to neurological rehabilitation, or appropriate for inter-disciplinary research (e.g., in *Scientific Reports*). Profs. [name] and [name] have been collaborating on stroke rehabilitation for close to a decade. They have jointly published papers in leading journals and conferences [e.g., 15-17] and have worked together in two funded research projects. [name] and [name] have collaborated on robotic rehabilitation, and have jointly supervised a student working on robotic mirror-game treatment [18].

Budget and matching funds: details and justification

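### Both hypotheses are tested on change scores without baseline adjustment, which over-corrects a chance baseline gap and loses precision unless the pre/post correlation is about 0.9 or higher

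*Combined protocol and SAP*

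**What the plan says.** The Data analysis section gives the whole statistical plan in a few sentences. For Hypothesis 1, "we will compare the change in the IP between the Pre-Test and the Post-Test as an indicator of motor improvement". A second Hypothesis 1 comparison, meant to capture learning, uses the IP difference between Post-Test and Follow-Up; paired t-tests are named for both. For Hypothesis 2, "changes in the area of the active control workspace and clinical scores will be compared between groups using paired t-tests". Normality is to be checked first. No covariate, regression model or site term is mentioned.

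The baselines exist. Under Research plan, Session 1 "will include a Reaching Pre-Test of 10 trials to a fixed target", which applies to both studies. In Study 2 a clinical evaluation precedes Session 1. Evaluations for Study 2 lists its content, repeated after training: FMA, Modified Ashworth score, TSRT and the active control workspace derived from it.

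On size and allocation, "we will test 24 healthy subjects and 24 patients who have moderate-to-severe stroke" and "Subjects will be randomly allocated to two equal groups". For Study 2 the two sites are pooled "for a total of 12 subjects per group". Under Subjects and subject recruitment, "Participants will be allocated by random numbers"; no stratification on a baseline value or on site is described.

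**The concern.** Subtracting the baseline is one way of using it, but it fixes the slope of post on pre at 1. When the true slope is below 1, the subtraction removes too much: an arm that happens to start lower is expected to gain more from regression to the mean alone, and that gain enters the group difference. The subtraction also adds the noise of the baseline measurement to the outcome. A model that estimates the slope avoids both.

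This is separate from the choice of a paired t-test, which cannot compare two independent groups. Replacing it with a two-sample t-test on change would make the comparison legitimate but leave this loss in place. What is at stake is the precision of the group difference, and its sensitivity to the luck of one small randomisation. According to the Knowledge translation section, that result is meant mainly to guide the design of a full trial.

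**Working it through.** The document gives no alpha, power, effect size, SD or pre/post correlation, so there is no stated figure to reproduce.

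**Inputs from the document.** Each study has 24 subjects in two equal groups, so n = 12 per arm.

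**Assumptions.** Equal SD before and after training (the unit below); pre/post correlation r from 0.3 to 0.95; two-sided 5% test.

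**Step 1: variance of the group difference.**

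- Change score: (2/n) × 2(1 - r).
- Baseline-adjusted: (2/n) × (1 - r²) × [1 + 1/(2n - 4)]. The bracket is the price of estimating the slope; at n = 12 it is 1 + 1/20 = 1.05.
- Ratio, adjusted to change: 1.05 × (1 + r)/2.

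| r | Variance ratio | Detectable difference at 80% power (SD), change vs adjusted | Power for an illustrative 0.8 SD effect, change vs adjusted |
|---|---|---|---|
| 0.3 | 0.68 | 1.42 vs 1.17 | 35% vs 48% |
| 0.5 | 0.79 | 1.20 vs 1.06 | 47% vs 56% |
| 0.7 | 0.89 | 0.93 vs 0.88 | 68% vs 72% |
| 0.8 | 0.94 | 0.76 vs 0.74 | 84% vs 86% |
| 0.9 | 1.00 | 0.54 vs 0.54 | 99% vs 99% |
| 0.95 | 1.02 | 0.38 vs 0.38 | near 100% for both |

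The t distribution has 22 degrees of freedom for change and 21 for the adjusted model. Break-even is where 1.05 × (1 + r)/2 = 1, so r = 2/1.05 - 1 = 0.90. A simulation of 20,000 trials at each r gave ratios of 0.79, 0.89 and 1.01 at r = 0.5, 0.7 and 0.9.

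**Step 2: chance baseline gap.** The SD of the difference in baseline means is √(2/12) = 0.408 SD. The chance of a gap above 0.5 SD in either direction is 2 × [1 - Φ(0.5/0.408)] = 0.22 per outcome.

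**Step 3: effect of a gap on the change score.** Given a gap g, the expected post difference is the true effect plus r × g. Subtracting g leaves the true effect minus (1 - r) × g. With g = 0.5 SD the shift is 0.25 SD at r = 0.5, 0.15 SD at r = 0.7 and 0.05 SD at r = 0.9, in the direction opposite to the gap. Averaged over randomisations g is zero, so the estimate is unbiased.

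**Step 4: adding site in Study 2.** With two covariates the bracket becomes 1 + 2/19 = 1.105. If site has no effect on outcome, the ratios are 0.83, 0.94, 1.00 (0.995 before rounding) and 1.05 at r = 0.5, 0.7, 0.8 and 0.9. Simulation with 12 subjects per site (an assumed split) gave the same values. Break-even is 2/1.105 - 1 = 0.81.

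**Step 5: which outcomes have a usable baseline.** IP, workspace area and FMA do. Borg effort is rated only at the end of each training session, so it has no pre-training value. The Modified Ashworth score is ordinal, from 0 to 4. The Post-Test to Follow-Up change starts from a value that training has already affected, so its starting point is not a randomisation baseline.

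**The case against.** The strongest case on the other side is that a two-sample comparison of change is valid, that r is unknown, and that the design makes a high r plausible: training lasts one week, IP rests on 10 trials, and patients are medically stable and no longer in treatment. At r = 0.8 adjustment saves only about 6% of variance. The study is preliminary and makes no power claim, so nothing stated is overturned, and the paired test in the same sentences is the more serious fault. All of this stands, and it limits the weight of the point. It does not remove the point: adjustment is better over most of the range of r and costs about 2% at worst within it.

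A reader might infer several stronger things that the document does not support:

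- *That chance imbalance is left uncorrected, or that the planned estimate is biased.* The change score does correct, but too much when r is below 1, and it is unbiased over randomisations. The shift is conditional on the gap that occurs.
- *That a material imbalance is likely.* A 22% chance of a gap above 0.5 SD is roughly one in five per outcome.
- *That precision is lost whatever the correlation.* The gain is gone at about r = 0.9, or about 0.8 if a non-prognostic site term is added.
- *That every outcome should be modelled on its Pre-Test value.* Borg effort has none. Modelling Follow-up on Pre-Test in place of the planned Post-Test to Follow-Up change would replace the quantity that the plan calls motor learning.

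**Conclusion.** The point holds, with conditions. The plan compares change scores without covariates although baselines for IP, workspace area and FMA are in hand. At 12 per arm this makes the variance of the adjusted estimate about 21% lower than that of the planned one at r = 0.5, 11% at r = 0.7 and 6% at r = 0.8, with no difference at about 0.9. It also leaves a conditional shift of (1 - r) times any baseline gap. The size rests on assumed r and equal pre and post SDs. This is a worthwhile improvement in efficiency and robustness, not a flaw that invalidates the comparison. It is best made together with the correction of the paired t-test.

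**What to change.** Change the wording of the Data analysis section as follows.

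- **Post-Test IP (both studies), post-training workspace area and FMA (Study 2):** replace the t-test on change with a linear model of the post value on group and the subject's own baseline value. Report the adjusted group difference with its 95% CI. The group term also supplies the between-group comparison that a paired t-test cannot give.
- **Motor learning:** keep the Post-Test to Follow-Up change, stated explicitly as a contrast between the two groups. If Follow-up IP adjusted for Pre-Test is added, label it as a separate estimand, the retained gain from baseline.
- **Borg effort and Modified Ashworth score:** do not apply the model to Borg effort, and do not rely on it for the Modified Ashworth score. Say how each will be compared.
- **Site in Study 2:** a site term is optional. Decide in advance, knowing that it lowers the break-even to about r = 0.8 if site is not prognostic.

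The cost is one degree of freedom for baseline (22 to 21 residual) and a variance increase of about 2% if r is near 0.95. No new data, visits or subjects are needed. The fitted model also provides the pre/post relationship and residual SD that planning the full trial will require.

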Studies suggest that errors made during training improve later performance of the task. For example, in a study in which elderly subjects practiced rhythmic motion of the upper limb with and without visual feedback, greater errors made during treatment led to more movement improvement following training (Levy-Tzedek 2017). This result is consistent with the TCT as muscle activation is regulated by the difference between the actual limb position and referent limb position specified by the brain. The referent position also plays a role in the perception of the actual limb position, while the afferent component identifies the deflection of the limb from the referent limb position. Based on this combination, the system identifies the movement error, i.e., deviation of the limb from the target position. Movement correction is accomplished by properly adjusting the referent limb position.

The sensitivity of referent control may be enhanced by augmentation of the movement error, i.e., Joint Error Augmentation (JEA). Furthermore an improvement in referent limb control is likely to be associated with improvement in threshold (referent control) at the level of individual joints. Development of rehabilitation treatment protocols based on motor control theory, such as that underlying JEA, is a promising direction for robotic rehabilitation therapy.

Research Objectives:

Our goals are to investigate the effect of JEA on motor learning in healthy subjects and on upper limb rehabilitation in subjects with stroke.

Hypothesis 1: In both groups, JEA applied to the elbow joint range will lead to better learning of movement speed and precision of a reaching task compared to no JEA.

Hypothesis 2: In patients with stroke, JEA applied to the elbow joint range will lead to a greater increase in the patient's active control zone at the elbow compared to no JEA and thus in his/her ability to perform isolated voluntary movement of the elbow.

Research plan

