The robotic system consists of an ergonomic double-joint horizontal manipulandum mounted on a rigid, movable support (Fig. 1). The subject sits in an armless chair with a high back support and trunk movement is restricted. The forearm is attached to the manipulandum with Velcro and the wrist and hand are free to move. Movements of the arm and manipulandum are used as input signals to move the arm avatar in the VR game. For the stroke group, the game (Fig. 2) is adapted to patient capabilities, based on her/his active control range for isolated elbow flexion and extension determined before each training session. The initial hand position is 10 cm sagittal to the patient's midline. Prior to

Session 1, a Pre-Test will be conducted in which subjects will reach 10 times to a fixed target placed at arm's length in the subject midline. The same protocol will be added to the end of Session 3 as a Post-Test and repeated 1 hour after Session 3 as the Follow-up Test.

Training Protocol: Objects to be reached are randomly presented within the virtual workspace every 2-10s. The subject is instructed to reach each object from the specified starting position as quickly and as accurately as possible in a session of at least 30 minutes (approximately 138 reaches, considering 3s/reach). To control training intensity, practice will be extended to the time needed to complete 138 reaches per session. During reaching, the motion of the whole arm is shown by an avatar, while vision of the subject's actual arm is blocked by a screen, to minimize visual-proprioceptive mismatch (Dietz 1992). For JEA trials, the avatar depiction includes a 10° elbow flexion error based on forward kinematic calculation. For implicit learning to occur,

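### The contrast labelled motor learning (Post-Test to Follow-Up) subtracts out the training gain, and no Pre-Test to Follow-Up comparison is planned

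*Combined protocol and SAP*

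**What the plan says.** Hypothesis 1 (Research Objectives) is that joint error augmentation (JEA) "will lead to better learning of movement speed and precision of a reaching task compared to no JEA". The Data analysis section addresses it with two contrasts in IP. The first is "the change in the IP between the Pre-Test and the Post-Test as an indicator of motor improvement". The second is "the change from Post-Test to Follow-Up as an indicator of motor learning".

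The timing of the tests is given in the session schedule under Research plan and again under Training protocol. The Pre-Test precedes all training. The fixed-target protocol is then "added to the end of Session 3 as a Post-Test and repeated 1 hour after Session 3 as the Follow-up Test". The session schedule agrees: once that session ends, "there will be a pause of 1 hour after the training and then a Reaching Follow-up Test of 10 trials to a fixed target". No training is described during the pause.

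The primary outcome is given only as change in IP, with no interval. No section plans a comparison of Pre-Test with Follow-Up, and none says which direction of Post-Test to Follow-Up change would count as learning.

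**The concern.** Learning is normally judged by how much of a gain over baseline is still there once practice has stopped. The planned learning contrast starts after practice has stopped, so it has no baseline in it and cannot show how much was learned. It describes the change over a one-hour pause, which may be decay, stability, offline gain or recovery from fatigue after a long session.

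Two things are at stake. First, the result reported under the heading of motor learning could be null, or could favour control, when JEA produced a larger and retained gain. Second, Knowledge translation states that "The preliminary results will primarily be used to inform the design of a full randomized controlled trial". A learning effect size taken from this contrast could mislead that design.

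**Working it through.** The plan gives no power, effect size, SD or retention figure, so there is no stated number to reproduce. The main point is algebra. The figures after it are illustrations.

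**Algebra.** Let G be the mean gain from Pre-Test to Post-Test in an arm, and r the fraction of it present at Follow-Up.

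- Pre-Test to Post-Test change: G
- Pre-Test to Follow-Up change: rG
- Post-Test to Follow-Up change: rG - G = -(1 - r)G

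With r = 1 the last line is 0 whatever G is. With G = 0 it is also 0. The score cannot tell these two cases apart.

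For the between-arm difference (J = JEA, C = control):

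- Planned learning contrast: (1 - rC)GC - (1 - rJ)GJ
- With equal retention r: -(1 - r)(GJ - GC), which is negative whenever r < 1 and JEA gained more
- Break-even retention for JEA: rJ = 1 - (1 - rC)GC/GJ

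**Inputs.** From the documents: 24 participants per study in two equal groups, so 12 per arm. Assumed: SD 1 for every change score, control gain GC = 0.5, JEA gain GJ = 1.3 (advantage 0.8) or 1.7 (advantage 1.2), and a two-sided 0.05 two-sample t-test. Power is from the noncentral t with 22 degrees of freedom and noncentrality d × √(12/2).

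**Equal retention in both arms.** Pre-Test to Post-Test power does not depend on retention. It is 47% at advantage 0.8 and 80% at advantage 1.2.

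| JEA advantage | Retention | Pre to Follow-Up: difference, power | Post to Follow-Up: difference | Significant for JEA | Significant for control |
|---|---|---|---|---|---|
| 0.8 | 100% | 0.80, 47% | 0 | 2.5% | 2.5% |
| 0.8 | 80% | 0.64, 32% | -0.16 | 1.0% | 5.7% |
| 0.8 | 60% | 0.48, 20% | -0.32 | 0.3% | 11.3% |
| 1.2 | 100% | 1.20, 80% | 0 | 2.5% | 2.5% |
| 1.2 | 80% | 0.96, 61% | -0.24 | 0.6% | 8.1% |
| 1.2 | 60% | 0.72, 39% | -0.48 | 0.1% | 20.2% |

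**When the contrast turns positive.** If control keeps 80%, JEA must keep more than 1 - 0.2 × 0.5/1.3 = 92%, or 1 - 0.2 × 0.5/1.7 = 94%. Just past that point there is almost no power. With control at 80% and JEA at 95%, the differences are +0.04 and +0.02 SD, significant for JEA in 3.0% and 2.7% of trials. Offline gain (110% in both arms) gives +0.08 and +0.12 SD, significant for JEA in 3.8% and 4.7%. Pre-Test to Follow-Up power in those two cases is 50% and 81%, then 54% and 87%.

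**The reverse error.** This is from a separate simulation with SD 1 at each test and correlation between tests of 0.5, 0.7 or 0.8. If JEA gains nothing while control gains 1 SD and loses all of it, Post-Test to Follow-Up is significant in favour of JEA in 65%, 85% or 96% of trials. The true Pre-Test to Follow-Up difference is 0.

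**The case against.** The strongest reply is that the two contrasts are meant to be read together. The first shows acquisition and the second shows whether it lasts, so a gain followed by no drop is evidence of learning. Their means also sum to the Pre-Test to Follow-Up change, so its point estimate can be recovered.

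Part of this stands. The training gain is tested, and a JEA advantage at the end of training would be seen. But the plan states no joint rule and attaches the word learning to the second contrast alone. A non-significant change with 12 per arm does not establish retention, and no equivalence margin is given. The sum gives an estimate of the retained gain but neither its confidence interval nor a test.

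A second reply is that the plan names paired t-tests and, for Hypothesis 1, does not say between groups, so the power figures describe a different analysis. That is true of the wording. However, Hypothesis 1 is a comparison with no JEA, and the algebra also applies within an arm: full retention gives an expected change of zero.

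A third reply is that the figures depend on assumed SDs. This also stands. At advantage 0.8 and 60% retention, setting the Post-Test to Follow-Up SD to 0.5 or 1.4 moves the rate favouring control from 11.3% to 32.3% or 7.7%. The sign does not change.

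Finally, this is a small preliminary study, and nothing says that an effect size will be taken from this particular contrast. That limits the harm but does not make the definition right.

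**Conclusion.** The concern holds. As written, the learning contrast excludes the gain that Hypothesis 1 is about, and the retained gain is not analysed. This conclusion needs only the timing of the three tests.

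The direction of the distortion depends on retention. With equal retention of at most 100%, the contrast is null or points against the arm that learned more. It favours JEA only if JEA retains proportionally more, past the break-even, or if there are offline gains. The sizes shown rest on assumed gains, SDs and retention, and should be read as illustration. The point should be fixed before analysis, because choosing the learning measure after seeing the data would weaken whatever is then claimed.

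**What to change.** In Data analysis, replace the Hypothesis 1 sentence with wording such as: *Motor learning is the between-group (JEA versus control) difference in Follow-Up IP, adjusted for Pre-Test IP by analysis of covariance. Pre-Test to Post-Test change is reported as acquisition. Post-Test to Follow-Up change is reported with its confidence interval as one-hour retention or decay.*

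A between-group comparison of Pre-Test to Follow-Up change would also serve, but one of the two should be named in advance. The text should state the one-hour interval wherever learning is claimed, since the study has no later test. Naming a between-group analysis also settles the paired t-test wording for this hypothesis.

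The cost is an edit to one sentence. All three tests are already scheduled, so no extra data, visits or participants are needed.
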